### Specific Aim 1: To quantify the short-term effect of T in infants with XXY on cardiometabolic outcomes.

**Hypothesis:** Percent body fat (%BF) will follow a normal trajectory in treated infants, while infants not receiving T will have greater %BF. **Approach:** In the TESTO: Testosterone Effects on Short-Term Outcomes trial, infants with XXY (n=75) age 4-12 weeks will be randomized 1:1 to receive 25mg intramuscular T injections every 4 weeks for 3 doses or placebo. %BF will be assessed by air displacement plethysmography at baseline, 12 weeks, and 24 weeks. The primary outcome is change in %BF z-scores at 12 weeks between groups (powered to detect a difference of 0.5SD). Infants initially receiving placebo will get T in the second half of the study (12-24 weeks). Secondary outcomes include change %BF z-scores from 12-24 weeks, growth parameters, and serum leptin.

**Specific Aim 2: To quantify the short-term effects of T in infants with XXY on neurodevelopment, gonadal function and safety outcomes.**

**Hypothesis:** (1): XXY infants receiving T will have greater gains in standard scores on early motor skills, emerging language, and adaptive functioning. (2): T treatment will not impair gonadal function, as measured by gonadotropins and biomarkers of Sertoli cell function. (3): There will be no serious adverse outcomes associated with T treatment in infants with XXY. **Approach:** Infants from Aim 1 will be given standardized neurodevelopment assessments at baseline, 12 and 24 weeks. Serum hormone biomarkers of gonadal function will also be obtained at these times. Adverse events will be monitored throughout the study.

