### B. Description of Population to be Enrolled:

A total of 75 infants with XXY will be enrolled. We will include all races, ethnicities, and languages.

*Inclusion criteria:* Male infants with 47,XXY karyotype identified prenatally who are 4-12 weeks old (31 to 90 days of age). 47,XXY must be from a diagnostic test such as CVS, amniocentesis, or post-natal blood/tissue. Non-invasive prenatal screening results alone will not be accepted.

*Exclusion criteria:*

- 1) >20% mosaicism for a normal cell line
- 2) Gestational age at birth <36 weeks
- 3) Birth weight <2.5thile or >97.5thile for age (small or large for gestational age)
- 4) History of thrombosis in self or a first degree relative
- 5) Exposure to androgen therapy outside the study protocol
- 6) Use of medications known to affect body composition, such as growth hormone or insulin
- 7) Known allergy to the testosterone cypionate solution components including benyl benzoate, benzyl alcohol, or cottonseed oil

Involving children is imperative as boys <18 years of age with XXY are much a different population than adult men with XXY. Men with XXY have been shown to have a high prevalence of type 2 diabetes, metabolic syndrome, fatty liver disease, and psychosocial difficulties. Clearly these processes begin in childhood. The potential to intervene in a preventative fashion, prior to the onset of disease, is more promising and productive than trying to treat pre-existing disease. Infant boys are exposed to endogenous testosterone in the first few months of life known as the “mini-puberty period of infancy.” Animal and human studies suggest this is a critical period for biologic programming, and therefore cannot be replicated at any other point in life. Including children in this study design allows us to investigate testosterone as a targeted intervention at this critical time point with evaluation of early markers of disease and disability. The ultimate goal is to improve the lives of children and adults with this condition.

The age of the infants at enrollment was chosen 1) to allow assessment of testicular function during the expected mini-puberty period of infancy, 2) to assure visits 2 and 3 will be completed before the infant is 10kg, as this is the upper weight limit for the PeaPod (our body composition assessment tool), and 3) feedback from parents.

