**Recruitment and Retention.** Methods of recruitment will include 1) approaching new and existing patients seen at CHCO clinics including the eXtraordinary Kids Clinic, Genetics Clinic, and Endocrinology Clinics, 2) outreach to the genetic counselors and obstetricians in the Denver metropolitan area who are ordering and interpreting prenatal testing results, 3) genetic counselors at CHCO who may receive calls/referrals for infants with XXY diagnoses, 4) Email and mailings to pediatric endocrinologists around the country (existing listserv) and through posting on the Pediatric Endocrinology Society active research website, 5) advertisements through the parent support group AXYS including websites, social media, emails, flyers, and mailings, 6) Email and mailings to prenatal genetic counselors throughout the country (existing listserv), and 7) study information on websites including Clinical Trials .gov, University of Colorado and Children’s Hospital of Colorado. To facilitate dissemination of information about our study, we will design study-specific webpage linked off the existing eXtraordinary Kids website.

The goal for recruitment will be 15 subjects per year in years 1-4. Based on our pilot study this goal is easily achievable. Modest travel expenses will be covered for out-of-state participants.

In between study visits, families may receive newsletters from the eXtraordinary Kids Clinic with updates from our ongoing research and periodic phone calls to stay in touch. Families will be invited to our eXtraordinary Party in conjunction with the bi-annual AXYS family conference.

**Enrollment in multiple clinical trials.** Enrollment in this protocol does not exclude participation in other clinical studies, with the exception of studies involving an intervention of androgen and/or other treatment that may impact body composition. Our team is concurrently enrolling for other studies involving infants with XXY, including the eXtraordinary Babies Study (COMIRB 17-0118). These studies are complementary and participants can enroll in either or both studies. If participants enroll in both studies, visits will be coordinated for convenience of the participant’s family and duplicate measures (ie blood draw, developmental testing, etc) will be combined.

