**F. Data Analysis Plan:**

The primary outcome for **specific aim 1** is the change in %BF z-scores between baseline and 12 weeks between treatment groups. Z-scores will be calculated using published norms for age, and the difference between groups will be assessed with a two-sided t-test using an alpha of 0.05. Allowing for a 10% drop-out rate, a sample size of 27 in each group gives us 80% power to detect a difference down to 0.5 z-score change between groups, and >99% power to detect the change score we observed in our pilot study (1.0 z-score change) assuming a variance of 0.65 per our pilot data. We will next use regression models with treatment group, baseline %BF, age of enrollment and feeding method as explanatory variables to assess absolute %BF at 12 weeks. Secondary analyses will include change in %BF z-scores from 12 to 24 weeks 1) in the group receiving T first (are the effects of T maintained or lost?) and 2) in the group receiving T second (does later T have the same effect?). We will analyze anthropometric measurements and serum biomarkers similarly.

For **specific aim 2**, the change in standard scores on developmental assessments will be analyzed in a similar fashion as in specific aim 1. Based on our pilot data, our sample size will yield 80% power to detect a difference between groups of 23 percentile points on the AIMS composite. Secondary analysis will include the changes in scaled scores for the individual Peabody domains and AIMS subtests, the Bayley composite scores, and the ABAS composite at 12 and 24 weeks. Gonadal function and safety outcomes will be compared between subjects on T and placebo using descriptive statistics.

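### The enrolment target of 75 does not match the 60 implied by Figure 6 and the power calculation, and the 0.65 labelled a variance reproduces the stated power only as a standard deviation

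*Combined protocol and SAP*

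**What the plan says.** Two places give a total of 75. Specific Aim 1 has "infants with XXY (n=75) age 4-12 weeks will be randomized 1:1", and section IV.B has "A total of 75 infants with XXY will be enrolled".

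Three places in the current text point to 60:

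- Figure 6 (section IV.C, Study Procedures) prints 30 for Group A and 30 for Group B.
- Section IV.F, on the primary outcome, says "Allowing for a 10% drop-out rate, a sample size of 27 in each group gives us 80% power"; the target difference is half a z-score.
- The recruitment paragraph in section IV.C says "The goal for recruitment will be 15 subjects per year in years 1-4".

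For the primary comparison, "the difference between groups will be assessed with a two-sided t-test using an alpha of 0.05". The spread is given as "assuming a variance of 0.65 per our pilot data". The pilot results in section III are printed as +0.86 ± 0.65 (untreated) and −0.24 ± 0.67 (treated), and the quantity after the ± is not named.

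**The concern.** There are two separate defects in the sample-size justification for the primary endpoint.

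First, a trial has one enrolment target. It determines when recruitment is complete, how many infants are exposed, and what power the trial has. Here the population section and the power section give different totals, with no reason for the difference.

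Second, a variance of 0.65 is a standard deviation of 0.806, about a quarter larger than 0.65. Required sample size scales with the variance, so the label changes the answer materially. Someone checking the calculation with the stated input gets neither the printed number per group nor the printed power, and could conclude that the trial is underpowered.

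**Working it through.** **Inputs.** Difference 0.5 z-score, two-sided alpha 0.05, power 80%, 27 per group, 10% drop-out and spread 0.65 (section IV.F). Total 75 (Specific Aim 1; section IV.B). 30 per group (Figure 6). Pilot spreads 0.65 and 0.67 (section III).

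**1. Sample size per group, normal formula:** n = 2 × (1.960 + 0.842)² × SD² / 0.5².

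- 0.65 as a standard deviation: 2 × 7.851 × 0.4225 / 0.25 = 26.5, so 27. This is the printed figure (28 by t-test).
- 0.65 as a variance: 2 × 7.851 × 0.65 / 0.25 = 40.8, so 41 (42 by t-test).

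**2. Power for 0.5 z at 27 per group.** Noncentrality is 0.5 / [SD × √(1/27 + 1/27)], with 52 degrees of freedom.

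- SD 0.65: noncentrality 2.83; power 79.2% by noncentral t, 80.7% by the normal formula. This reproduces the stated 80% to rounding.
- Variance 0.65 (SD 0.806): noncentrality 2.28; power 60.9% by t, 62.5% normal.

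**3. The claim of more than 99% power for a 1.0 z-score difference.** At 27 per group, power by t is 99.98% with SD 0.65 and 99.4% with variance 0.65. The claim holds either way, so it does not settle the label. Only the 27 and the 80% do.

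**4. Enrolment.**

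- 27 / 0.9 = 30 per arm; 2 × 30 = 60, in agreement with Figure 6.
- 15 per year × 4 years = 60. This is supporting evidence only: Table 1 lists five study years and its enrolment cells cannot be read.
- If 27 were the number enrolled per arm, about 24 would be evaluable, power with SD 0.65 would be about 74% by t (76% normal), and the total of 54 would match neither 60 nor 75. So 27 is the evaluable number.
- 75 × 0.9 = 67.5, so about 67 evaluable, split 34 and 33.
- To finish with 54 evaluable out of 75, loss would have to be 1 − 54/75 = 28%, not 10%.

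**5. Power for 0.5 z under each enrolment total, 10% loss, by t:**

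| Spread assumed | 60 enrolled (27/27) | 75 enrolled (34/33) |
|---|---|---|
| SD 0.65 | 79.2% | 87.3% |
| SD 0.67 | 76.8% | 85.3% |
| Variance 0.65 | 60.9% | 70.6% |

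With SD 0.65, the difference detectable with 80% power is 0.505 z at 27/27 and 0.452 z at 34/33.

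**The case against.** The best reply is that enrolling more than a calculated minimum is not an error. Section IV.F says what 27 per group delivers; it does not say that only 60 will be enrolled, and 75 infants meet that requirement with room to spare. Five study years at 15 per year would also give 75, so the target may have been raised and Figure 6 left behind. The variance label looks like a slip, because section III prints the same 0.65 after a ± sign, the usual way to show a standard deviation. On this view nothing in the conduct or analysis changes.

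Much of that is fair. There is no loss of power if 0.65 is a standard deviation, and the correction is editorial. But the recruitment goal is limited to years 1-4, Specific Aim 1 says that the 75 are randomised (so screening losses do not explain the gap), and no reason for the larger total is given. Calling the label a slip concedes that the text is wrong as printed.

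Two smaller points also stand. The exact 27 comes from the normal formula; under the planned t-test the requirement is 28, a rounding-level difference. The 34/33 split assumes near-equal arms. With blocks of 20, a total of 75 ends mid-block and the arms could differ somewhat, but power stays at about 87-88%.

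**Conclusion.** The point holds. The current text gives two enrolment totals, 75 and 60, and the stated power belongs to the smaller one. The input labelled a variance reproduces the printed 27 per group and 80% only as a standard deviation. That reading is an inference: it rests on matching both printed figures and on the ±0.65 in section III, and it should be confirmed against the pilot data.

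If it is confirmed, a 75-infant trial with 10% loss has about 87% power for 0.5 z, more than stated, and a 60-infant trial has the stated 80% to rounding. If 0.65 really were a variance, neither total would supply the 42 evaluable infants per arm needed for 80% power by t-test. That is why the label needs correcting even though the standard-deviation reading is much the more likely. These figures assume equal spread in the two arms, near-equal arm sizes and 10% loss.

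**What to change.** 1. Choose one enrolment target. State it with its drop-out assumption, evaluable number per arm and power, and use the same figures in Specific Aim 1, section IV.B, the recruitment goal and Figure 6 in section IV.C, and section IV.F.
   - If 75 with 10% drop-out is intended: about 33-34 evaluable per arm and about 87% power for 0.5 z (80% power at about 0.45 z), with Figure 6 and the recruitment goal changed to match.
   - If 60 is intended: keep 27 per group and 80%, say that this is the normal-formula result (79.2% by t-test), and change the total in Specific Aim 1 and section IV.B.
   - If 75 was chosen so as to finish with 27 per arm: state the implied 28% loss in place of 10%.
2. In section IV.F, relabel 0.65 as a standard deviation once it has been checked against the pilot data, and name the measure of spread in section III.
3. Check the Aim 2 power sentence in section IV.F, because its 23 percentile points on the AIMS depend on the same sample size. If 23 was computed at 27 per group (an assumption; the plan does not say), the corresponding figure at 34/33 is about 23 × 0.452/0.505 = 20.6.

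The cost is protocol wording only. The correction itself calls for no infants beyond the 75 already stated, and no change to the endpoint, test or alpha.

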### III. Preliminary Studies/Progress Report:

**Preliminary data to support the study concept: We have found testicular and cardiometabolic function are inversely related in pre-pubertal XXY boys, and androgen supplementation improves cardiometabolic markers.** In a study of 93 boys with XXY age 4-12 (NCT00348945), 20% had evidence of testicular failure (low INHB) at baseline, as well as elevated percent body fat (%BF, z-score +1) and high prevalence of metabolic syndrome features. Low INHB was associated with greater cardiometabolic risk including higher blood glucose, triglycerides, and low-density lipoprotein (LDL), and lower high-density lipoprotein (HDL), all  $p < 0.05$ . This is evidence that both testicular and cardiometabolic function is impaired before puberty in boys with XXY. Furthermore, two years of treatment with a weak androgen improved body composition (Figure 3) and cardiometabolic markers.

**Figure 3.** %BF is high in XXY boys 4-12 yrs old. Androgen therapy improves body composition ( $p=0.04$ ).

**Preliminary data to support the study design: Our pilot study suggests this regimen of T is well tolerated and does affect body composition.** In preparation for this study, I designed a feasibility study to evaluate the short-term effects of T on body composition (COMIRB 14-7240, NCT02408445) in infants. We enrolled 18 infants with XXY between 6-15 weeks of age and randomized subjects to receive testosterone cypionate 25mg intramuscularly every 4 weeks x 3 or no treatment. I hold an Investigational New Drug (IND 124260) file for the use of T in infants with XXY, and this file will be updated with this protocol. There have been no serious adverse events and the only side effects were an increase in appetite ( $n=2$ ) and acne ( $n=2$ ). %BF at baseline was normal, however increased by a z-score of  $+0.86 \pm 0.65$  over 12 weeks in infants not receiving T, while the change in %BF z-scores for infants who received T was  $-0.24 \pm 0.67$  (Figure 4). XXY infants who did not receive T had 4% more body fat at 5 months of age than normal male

**Figure 4. Left:** T shots favorably effect the change in %BF z-scores after 12 weeks in infants with XXY. **Right:** At 5 months (visit 2), %BF is 4% higher in XXY boys not treated with T compared to 316 healthy boys.

infants in the local Healthy Start Study.

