### C. Study Design and Research Methods

**Overall study design.** TESTO is a randomized controlled trial assessing the efficacy and safety of T injections in infants with a prenatal diagnosis of XXY. Body composition, neurodevelopment, serum hormones, safety parameters, and metabolomics will be assessed at baseline, 12 and 24 weeks into the

study. Infants will be randomized 1:1 to receive T vs placebo for the first 12 weeks of the study with the primary outcomes assessed after 12 weeks (Figure 5). The second half of the study will cross the treatment groups allowing us to evaluate if timing makes a difference in response and if initial benefits are sustained. This plan will optimize enrollment, as many parents will only participate if their son will get treatment, and allow us to maintain the blinded design.

**Setting.** The study will be conducted at Children’s Hospital Colorado (CHCO) in the outpatient Pediatric Clinical Translational Research Center (CTRC). CHCO is home to the eXtraordinary Kids Clinic, the first comprehensive interdisciplinary clinic for sex chromosome aneuploidies. The unique collaborative model and our expertise has led to national referrals and a high demand for clinical evaluations. We have successfully recruited hundreds of boys with XXY to participate in longitudinal and interventional research studies through close collaboration with family support groups and national/international experts in XXY. Our investigative team has expertise in child development, infant body composition, childhood disorders of insulin resistance, metabolomics, clinical trial recruitment, robust data acquisition and data analysis, making this the ideal setting.

[figure not shown]

Figure 5. Overall Study Design

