#### **E. Potential Scientific Problems:**

Recruitment and retention of subjects with rarer pediatric conditions can be problematic, however with our successful feasibility study and accommodation for participant travel in this budget, we do not anticipate enrollment as an obstacle. Utilizing a cross-over-type design reduces our major parental reservation of the study, which is the possibility of being randomized to not receive T, and still allows us to evaluate short-term effects of T and observe the metabolic pathways that have been altered. As with all clinical research, we acknowledge there will be ascertainment bias and strict inclusion criteria that may limit the generalizability of our results. Our proposal only includes prenatally diagnosed infants, however our previous work demonstrated no differences in cardiometabolic or gonadal function between pre- or postnatally diagnosed XXY boys therefore results from these outcomes should be generalizable. Finally, to further assess the external validity of our study we will collect and compare basic demographic data from families who decline study participation, and will also compare our study cohort to our historic data of infants who are seen in our eXtraordinary Kids Clinic.

Results and interpretation from the second half of the participant protocol (weeks 12-24) does require certain assumptions, including that this larger study finds similar differences in body composition between treated and untreated infants as our pilot study did. There will not be a control group as part of this study for the second half of the study, but importantly these outcomes are all secondary. In addition, we are concurrently recruiting for a natural history study in infants with X&Y chromosome variations (eXtraordinary Babies) that includes 100 infants with XXY who will have body composition assessments (PeaPod and later DEXA). Some of these will be infants participating in this study, but presumably an important subset will not be in the TESTO study and will not have received testosterone clinically. Finally, data from the Health Start Study of healthy local infants can serve as a non-XXY control group for normal adipose accumulation in infancy.

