For **specific aim 3 (exploratory)**, we will compare C14:1 concentrations (an easily identified LCAC) between treatment groups at 12 weeks using two-sided t-tests, hypothesizing C14:1 will be lower in the T treated group (representing improvement in fatty acid oxidation and energy metabolism). This aim is exploratory; with 10 subjects per group we will have 80% power to detect a difference of 1.3 SD with a two-sided alpha of 0.05. Then, paired t-tests will be used to compare C14:1 before and after T treatment (5 paired samples), with similar power. We will analyze secondary outcomes including other LCAC and BCAA (leucine, isoleucine, and valine) in a similar fashion. Next, we will use principle component analysis on the entire dataset from the comprehensive untargeted analysis to identify patterns and pathways altered with T treatment. The spectra data file from the non-targeted metabolomics panel will be uploaded to MetaboAnalyst, and the software will be used for Metabolite Set Enrichment Analysis as well as Pathway Enrichment Analysis. We will have >80% power to detect at least 2-fold changes between T treated and untreated using a significance level of 0.0001 (less than two false positives based on the conservative Bonferroni correction for multiple comparisons). We will also input the analytes into known KEGG pathways of energy metabolism to look for pathway enrichment.

Table 2. Summary of primary and secondary outcome measures for each Specific Aim (SA).

SA	Primary Outcome	Weeks		Measurement Tool
		12	24	
SA 1: Cardiometabolic	Change %BF z-scores from baseline	X		PeaPod
	Secondary Outcomes			
	Change %BF z-scores from baseline		X	PeaPod
	Change in height, weight, weight-for-length and waist circumference z-scores from baseline	X	X	Physical exam measurements
	Serum leptin, lipids, and insulin	X	X	Immunoassays in CCTSI core laboratory
SA 2	Primary Outcome			

	Change in motor composite from baseline	X		AIMS percentile composite score (all domains)
	Secondary Outcomes			
	Serum LH, FSH, INHB, AMH, E2 and Total T	X	X	Immunoassay and LC/MS ([name] lab)
	Change in gross and fine motor scaled scores	X	X	Scaled scores on all PDMS-2 domains, AIMS
	Cognitive and Language composite scores	X	X	Bayley III: cognitive and language domains
	Adaptive functioning	X	X	ABAS III standard scores
	Number of adverse events	X	X	Verbal questionnaire, parent-report
SA 3: Metabo- Iomics	Primary Outcomes			

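### The two second-half questions rest on uncontrolled within-arm %BF z-score changes from week 12 to week 24, which can be misread if untreated infants drift; a randomised week-24 contrast should be prespecified

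*Combined protocol and SAP*

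**What the plan says.** Section IV.C gives the second half a scientific purpose: crossing the groups is meant to "evaluate if timing makes a difference in response and if initial benefits are sustained".

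Section IV.F (specific aim 1) is the only place where an analysis is attached to that purpose. It takes the %BF z-score change from week 12 to week 24 separately "in the group receiving T first (are the effects of T maintained or lost?) and 2) in the group receiving T second". The question for the second arm is put "in the group receiving T second (does later T have the same effect". It names no between-arm comparison, reference trajectory, test or decision criterion for these weeks.

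Section IV.E concedes the limitation: "There will not be a control group as part of this study for the second half of the study". It adds that interpretation needs assumptions and that the outcomes concerned are secondary. It names two outside sources of comparison, an XXY natural history cohort that partly overlaps with this trial and a cohort of healthy local infants. Neither appears in IV.F or Table 2.

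The 24-week %BF outcome is also defined in two ways. Specific Aim 1, IV.A and IV.F use the change from week 12 to week 24. Table 2 lists "Change %BF z-scores from baseline", marked at week 24.

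**The concern.** A change within one arm answers a causal question only if one knows what that arm would have done otherwise. Z-scores against healthy-infant norms would supply this if untreated XXY infants held a constant z-score. The pilot in section III suggests that they do not: the mean rise was 0.86 z "over 12 weeks in infants not receiving T", against -0.24 z with T.

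If some of that drift continues past week 12, the T-first arm will rise even when its advantage over untreated infants is intact, and the rise can be taken for loss of benefit. In the T-second arm the same drift offsets the T effect, so later T can look weaker than early T when it is not. Early versus delayed T is the question that the crossing was designed to address, and section IV.G says that the results will inform clinical management.

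**Working it through.** **Inputs.** Pilot change over weeks 0 to 12 (section III): untreated +0.86 (SD 0.65), treated -0.24 (SD 0.67). From IV.F: 27 per arm, two-sided alpha 0.05, variability 0.65. Untreated drift after week 12, written d, is not given. I assume 0 to 0.86 z, the upper end being the pilot's value for weeks 0 to 12.

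**The plan's own figure.** n per arm = 2(1.96 + 0.84)² × 0.65² / 0.5² = 26.5, so 27. Power at 27 per arm for 0.5 z is 81% by the normal approximation and 79% by the noncentral t. The stated 80% is reproduced if 0.65 is an SD. IV.F calls it a variance; read literally, the SD is √0.65 = 0.806 and power is 61% (noncentral t). I use 0.65 and show 0.806 alongside.

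**T-first arm, advantage over untreated infants fully kept.** The expected within-arm change is then d. IV.F names no test for this, so I assume a paired t-test with n = 27. SE = 0.65/√27 = 0.125, or 0.155 with SD 0.806. Probability of a significant result:

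| d (z) | SD 0.65 | SD 0.806 |
|---|---|---|
| 0 | 5% (either direction) | 5% |
| 0.20 | 34% | 24% |
| 0.30 | 64% | 46% |
| 0.36 | 79% | 61% |
| 0.43 | 91% | 76% |
| 0.86 | >99% | >99% |

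**T-second arm, late effect equal to the pilot's.** Pilot effect = -0.24 - 0.86 = -1.10 z. Expected within-arm change = -1.10 + d: -1.10 at d = 0, -0.67 at d = 0.43 and -0.24 at d = 0.86.

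**What randomised contrasts estimate.** Let E be the early T effect, R any rebound after early T stops, L the late T effect, d₀ the untreated drift in weeks 0 to 12, and d the drift in weeks 12 to 24, taken as common to both arms.

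- Baseline to week 24: T-first = d₀ + E + d + R; T-second = d₀ + d + L. The difference is E + R - L, and drift cancels.
- Weeks 12 to 24 only, T-second minus T-first: (d + L) - (d + R) = L - R. Drift cancels, but the late effect is mixed with rebound.

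The first is a valid comparison of early with delayed T. It equals zero if the early effect persists and late T matches it (R = 0, L = E). It also equals zero if the early effect vanishes and late T does nothing (R = -E, L = 0). It therefore cannot separate persistence from catch-up.

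**Precision of the week-24 contrast.** If the 24-week change also has SD 0.65, SE = 0.65 × √(2/27) = 0.177 z and power for 0.5 z is 79%. With SD 0.806 it is 61%. The documents give no SD for 24-week change.

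**Age at week 24.** Section IV.D says the norms cover birth through 6 months. The youngest entrant is 31 days old and the visit window is ±10 days, so the earliest week-24 visit falls on day 31 + 168 - 10 = 189, about 6.2 months. The nominal age in IV.C is about 8 months. Every week-24 z-score thus lies beyond the cited norms. Extrapolation error would pass straight into a within-arm change and would largely cancel between randomised arms.

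**The case against.** The strongest reply is that the protocol already says this. IV.E states that there is no control in the second half, that assumptions are needed and that the outcomes are secondary, and it points to XXY infants outside the trial who could show the untreated course. The disclosure stands and limits how serious the point is. It does not settle it, because IV.F gives no method for using the outside cohorts. They are also non-randomised, and one is non-XXY. The assumption IV.E names, a pilot-like treatment difference, is not the one a within-arm reading needs, which is no drift after week 12.

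A second reply concerns what counts as maintained. Specific Aim 1 hypothesises that treated infants follow a normal trajectory. By that yardstick a rising z-score after T stops is a departure, and calling it loss is defensible. That is fair. My calculation defines maintained as keeping the advantage over untreated XXY infants. The plan does not say which meaning it intends.

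Three stronger readings are tempting, and the documents do not support them:

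- That the plan will reach a wrong answer. Drift after week 12 is unknown, the 0.86 comes from an 18-infant pilot at a younger age, and at d = 0 there is no bias.
- That the plan prescribes a faulty within-arm test. It gives no test or criterion for weeks 12 to 24; the paired t-test is my assumption.
- That anthropometry and biomarkers are equally affected. IV.F says they will be analysed similarly, but IV.A and Table 2 already define anthropometric change from baseline to 12 and 24 weeks.

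**Conclusion.** The point holds in a limited form. The only analyses written for the two second-half questions are uncontrolled changes within each arm, and drift of the kind seen in the pilot can be misread as lost benefit or as a weaker late effect. Over the assumed drift of 0 to 0.86 z, the chance of a significant change in a T-first arm that has kept its advantage runs from 5% to over 99%, and a late effect of -1.10 z can appear as small as -0.24. These figures rest on 27 per arm, SD 0.65, a paired t-test, and maintained meaning an advantage kept over untreated infants. The primary 12-week comparison is untouched. This should be changed, but the outcomes are secondary and the limitation is disclosed, so it does not threaten the trial's main conclusion.

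**What to change.** In IV.F, prespecify the randomised T-first versus T-second contrast of %BF change from baseline to week 24 as the secondary test of early versus delayed T. Align Specific Aim 1, IV.A and IV.F with the Table 2 definition.

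Because the cited norms stop at 6 months, run this contrast on absolute %BF adjusted for baseline %BF and age, or on z-scores from norms that cover the visit age. The first option extends the regression that IV.F already plans at 12 weeks.

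Report the within-arm 12-to-24-week changes descriptively, along with any between-arm difference in those changes, and draw no conclusion from one arm that benefit was maintained or lost or that later T had the same effect. If the natural history cohort is to inform the untreated course, state which infants qualify and how they will be used.

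No new visits or infants are needed. The costs are a change of wording, a choice of %BF scale at week 24, and a narrower claim, since the contrast cannot separate persistence of the early effect from catch-up in the late-treated arm. Power is about 79% for 0.5 z only if the 24-week SD is also 0.65 (61% if 0.806). These z-score figures do not carry over to absolute %BF, for which the documents give no SD.
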